The **long-term** goal of our research is to improve tobacco dependence treatment outcomes for AA smokers by identifying promising interventions. The **objective of this project** is to examine the efficacy of optimized (OPT) versus enhanced usual care (UC) treatment for smoking cessation. Optimization interventions have been widely used in other disciplines but are relatively new to tobacco dependence research. Given that tobacco dependence is a chronic, relapsing disorder characterized by multiple failed quit attempts, the high degree of heterogeneity in treatment response, and the absence of new pharmacotherapy advances, the best opportunities to improve tobacco treatment for AA smokers lie in the use of novel methodologies that explore how to optimize treatment through providing smoking cessation counseling while altering the timing, sequencing, or combining of existing pharmacotherapies to maximize efficacy. Consequently, AA smokers randomized to opt (n=196) will receive high intensity smoking cessation counseling, nicotine patch (NP), and up to two pharmacotherapy optimizations [bupropion (BUP), varenicline (VAR)] based on verified smoking status at Weeks 2 and 6. AA smokers randomized to enhanced UC (n=196) will receive the same high intensity counseling and NP with no optimizations in

pharmacotherapy. The **central hypothesis** is that OPT will result in significantly higher abstinence rates relative to UC.

Our specific aims are:

- 1) Evaluate the short- and long-term efficacy of optimized pharmacotherapy for smoking cessation in AA smokers.** Hypothesis 1: Participants randomized to OPT will have significantly higher biochemically-verified abstinence at Week 12 (primary endpoint) than participants randomized to UC. Hypothesis 2: Participants randomized to OPT will have significantly higher biochemically-verified abstinence at two follow-ups, Week 18 and Week 26, than participants randomized to UC.

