The above studies support the strong scientific premise for an optimized approach to tobacco dependence treatment. Notably, 70-91% of participants in the above studies have been White smokers.³⁹⁻⁴³ AAs have different smoking patterns and behaviors, including a preference for

menthol cigarettes, fewer CPD, and different preferences for and responses to pharmacotherapy, including differences in nicotine and pharmacotherapy metabolisms.^{12,15,19,46-48} Therefore, the selection and sequence of smoking cessation medications

II. Research Plan and Design

A. Study Objectives

The objective of this study is to examine the efficacy of optimized (OPT) versus enhanced usual care (UC) treatment for smoking cessation. AA smokers randomized to OPT (n=196) will receive high intensity smoking cessation counseling, nicotine patch (NP), and up to two pharmacotherapy optimizations [bupropion (BUP), varenicline (VAR)] based on verified smoking status at Weeks 2 and 6. AA smokers randomized to enhanced UC (n=196) will receive the same high intensity counseling and NP with no optimizations in pharmacotherapy.

B. Study Type and Design

The proposed study is a randomized adaptive treatment trial for smoking cessation in 392 AA smokers. Participants randomized to OPT (n=196) will receive smoking cessation counseling, nicotine patch and up to two pharmacotherapy adaptations (VAR, BUP+NP) based on verified smoking status at Weeks 2 and 6. Participants randomized to UC (n=196) will receive the same smoking cessation counseling and NP; pharmacotherapy in this group will not be optimized. Pharmacotherapy and counseling in both groups will last for 18 weeks with long-term follow-up through Week 26. The primary outcome is biochemically-verified smoking status at Week 12.

C. Sample size, statistical methods, and power calculation

392 eligible AA smokers will be randomized. We will use a 1:1 fashion to either OPT or enhanced UC. Randomization will be stratified based on to ensure an equal proportion of male and female smokers in OPT and UC. Randomization will be determined by computer-generated random numbers. Randomization assignments will be placed in sealed envelopes with sequential study ID numbers. After baseline data collection has been completed, the research assistant will select the sequential study ID number to determine the randomization assignment.

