The primary endpoint is urine anatabine and anabasine-verified 7-day point prevalence abstinence at Wk 12. While CO is used for adaptation decision making, the more robust anatabine/anabasine are being used for biochemical verification of study endpoints, with the recommended cut-off of 2 ng/ml to differentiate smokers from non-smokers.⁶⁰ These tobacco alkaloids are the gold standard for confirming abstinence when participants are on NRT and cotinine measurements are invalid because detectable levels of cotinine could reflect NRT use or smoking.⁶⁰ We expect an 18% cessation rate at Wk 12 in the UC group and a 32% cessation rate in the OPT group. This difference in cessation is consistent with an adaptive trial which found that 10% of smokers who failed on one therapy and were switched to another early in treatment were rescued after one adaption.³⁵ Given two optimizations in the current study, we expect that ~15% of smokers will be rescued at Week 12 in OPT relative to UC. Using the chi-square test, along with 18% and 32% cessation rates, 196 participants in each group will give us 90% power to detect this difference with a type I error rate of 5%.

D. Subject Criteria (See Vulnerable Populations appendix, if applicable)

Participants will be AA adults over the age of 18 who smoked cigarettes daily at enrollment and have smoked at this rate for \geq 6 months. The study will be open to both men and women. We have chosen to focus on AAs only because their unique smoking profile places them at greater risk for tobacco-related disease and death.

Eligibility Criteria

Inclusion Criteria	Exclusion Criteria

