Final Screening and Enrollment (Wk 0). Final eligibility screening will be conducted in person and will consist of a pregnancy test on women of childbearing age and obtaining informed consent.

Counseling Visits (Wks 0, 1, 2, 3, 6, 7, 12). Counseling sessions, each lasting approximately 20 minutes, will be completed in person at Wks 0, 2, 6, 12 and by telephone at Wks 1, 3, 7. The number of sessions is consistent with our previous studies where we have achieved visit completion rates of ~ 80%.^{12,14,15,19}

Response/Non-Response to Pharmacotherapy (Wk 2, 6). Exhaled air carbon monoxide

(CO) is an immediate, non-invasive method of biochemically verifying smoking status. At Wk 2 and 6, all participants will breathe into a Micro-3 Smokerlyzer (Bedfont Scientific) for the purpose of determining abstinence. All participants will be informed of their CO level and it will be used to frame counseling discussions around smoking status/quitting. OPT participants with CO LTE 5 ppm will be considered 'responders' and will continue on their existing pharmacotherapy. Those with CO GT 5 ppm will be considered 'non-responders' and will be switched to the next pharmacotherapy per Figure 1.

Medication Dispensing (Wk 0, 2, 6, 12).

Medication will be dispensed at Wk 0 (baseline) and Wk 2, 6, 12 in the quantity needed to get participants to the next assessment/optimization time

point. This approach has resulted in 88% attendance at medication dispensing visits in our previous studies. Participants will be asked to return unused medication to ensure (a) that OPT participants take only the medication corresponding with the current stage of treatment and (b) that OPT and UC participants on NP receive a supply that corresponds with their current dosing needs. Those who do not attend medication dispensing visits will be mailed enough of their *current* medication to get them to the next dispensing time point. Participants must be eligible for NP, BUP, and VAR as a condition of eligibility; however, prior to switching, we will reassess medical eligibility in OPT non-responders. Given the short time frame between visits and careful upfront screening, we expect that very few non-responders will be medically ineligible for switching. Those who are will either receive the next therapy for which they are eligible (BUP, VAR) or, if medically ineligible for either switch, stay on their existing pharmacotherapy.

COVID-19 Remote Visits.

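### Does the missing rule for participants without a Week 12 urine sample leave the primary result open?

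*Combined protocol and SAP*

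**What the plan says.** The primary outcome appears in three places.

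- Hypothesis 1 in I.A: "Participants randomized to OPT will have significantly higher biochemically-verified abstinence at Week 12 (primary endpoint) than participants randomized to UC".
- II.B: "The primary outcome is biochemically-verified smoking status at Week 12".
- II.C: "The primary endpoint is urine anatabine and anabasine-verified 7-day point prevalence abstinence at Wk 12".

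II.C expects 18% cessation with usual care (UC) and 32% with optimised treatment (OPT), tested by chi-square, and concludes that "196 participants in each group will give us 90% power to detect this difference with a type I error rate of 5" per cent. V.A and V.B add nothing and send the reader back to II.C.

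No section names the analysis set or says what happens when there is no Week 12 urine. The plan does expect absences. Week 12 is a medication dispensing visit, and II.E (Medication Dispensing) reports of such visits: "This approach has resulted in 88% attendance at medication dispensing visits in our previous studies". It continues: "Those who do not attend medication dispensing visits will be mailed enough of their" current medication to reach the next dispensing point. Absentees therefore have a medication rule but no written outcome rule.

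**The concern.** Two rules are in common use. One divides verified quitters by everyone randomised, so that a missing sample counts as smoking. The other divides by those who gave a sample. If return is equal in the two arms the choice hardly affects the test. If return is unequal, the same data can be significant under one rule and not under the other, and a rule chosen once return by arm is known could then settle the primary result.

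Unequal return is conceivable. Treatment differs visibly between arms. Under II.E "All participants will be informed of their CO level", and OPT non-responders are switched, while for UC II.B says "pharmacotherapy in this group will not be optimized". At 88% attendance, 392 x 0.12 = about 47 participants would have no sample. The II.B wording adds some doubt, because smoking status without a urine is unknown, whereas verified abstinence without a urine is simply not achieved.

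**Working it through.** **Inputs.** 18% v 32%, 196 per arm, type I error 5% (II.C; two-sided assumed, since sidedness is not stated). The documents give no Week 12 urine return. The nearest figures, both in II.E and both from earlier studies, are 88% (dispensing visits) and about 80% (visit completion, quoted for the counseling schedule). Their use as return rates here is an assumption.

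**1. The plan's own power.** With the pooled chi-square:

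- SE under the null = sqrt(2 x 0.25 x 0.75 / 196) = 0.0437
- SE under the alternative = sqrt((0.18 x 0.82 + 0.32 x 0.68) / 196) = 0.0432
- z = (0.14 - 1.96 x 0.0437) / 0.0432 = 1.26, so power = 89.6%

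With the unpooled variance it is 90.0%. The stated 90% is reproduced with all 196 per arm in the denominator.

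**2. Equal return.** Let a fraction r return urine in each arm, and let p be the pooled abstinence rate among returners. The ratio of the two test statistics, missing-equals-smoking over complete-case, is sqrt((1 - p) / (1 - rp)). At r = 0.88 and rp = 0.25, p = 0.284 and the ratio is sqrt(0.716 / 0.75) = 0.98. The tests nearly coincide. For example, with 172 returning per arm and 31 UC quitters, no OPT count gives different verdicts.

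**3. Unequal return: constructed examples.** Pearson chi-square without continuity correction.

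| Return UC / OPT | Complete-case | p | Missing = smoking | p |
|---|---|---|---|---|
| 88% / 80% | 31/172 v 44/157 (18.0% v 28.0%) | 0.031 | 31/196 v 44/196 (15.8% v 22.4%) | 0.095 |
| 80% / 88% | 28/157 v 44/172 (17.8% v 25.6%) | 0.090 | 28/196 v 44/196 (14.3% v 22.4%) | 0.037 |
| 90% / 86% | 32/176 v 47/169 (18.2% v 27.8%) | 0.033 | 32/196 v 47/196 (16.3% v 24.0%) | 0.059 |

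First row in full, complete-case: difference 0.100, pooled rate 75/329 = 0.228, SE = sqrt(0.228 x 0.772 x (1/172 + 1/157)) = 0.0463, chi-square = (0.100/0.0463)^2 = 4.67. Over all randomised: difference 0.0663, pooled rate 75/392 = 0.191, SE = 0.0397, chi-square = 2.79.

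Each example has an observed OPT rate among returners of 25.6-28.0%, below the planned 32%. With 18% and 32% among returners, UC 88% / OPT 80% gives p = 0.004 and p = 0.018, so both rules are significant.

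**4. How often the rules disagree.** Exact binomial enumeration with return counts fixed, 18% and 32% taken as rates among all randomised, and returner rates therefore 0.18/r(UC) and 0.32/r(OPT):

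| Return UC / OPT | Trials in which the rules differ on significance |
|---|---|
| 88% / 88% | 0.8% |
| 90% / 86% | 3.7% |
| 86% / 90% | 3.9% |
| 94% / 88% | 5.3% |
| 88% / 94% | 7.7% |
| 88% / 80% | 6.5% |
| 80% / 88% | 10.8% |

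The probability of significant results in opposite directions is zero in every row.

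**5. If 18% and 32% were rates among returners.** At equal 88% return, power would be 84.0% with missing = smoking (15.8% v 28.2% of 196) and 85.4% complete-case (172 per arm).

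**The case for a change.** The best case for a change is that an implied rule is not a written one. A complete-case chi-square would contradict no sentence of the plan, and writing the rule down would cost almost nothing. The choice also matters most when the result is close: with a true OPT rate of 27% among all randomised, the rules disagree in 17-20% of trials at 88% / 80% return in either direction. Nor is missing-equals-smoking neutral. With 18% abstinence among returners in both arms and return of 80% UC / 88% OPT, it favours OPT significantly in 5.4% of trials instead of 2.5%.

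The omission stands, and so does the arithmetic. Three things limit its weight.

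- The imbalance is built by giving one arm the 88% figure and the other the 80% figure. These are pooled figures for different kinds of visit, not an arm difference. Being told the CO level, the reminders and the Week 12 payment are the same in both arms.
- The 5.4% is a false-positive rate only if missing participants quit at the same rate as returners. If they are in fact smoking, true abstinence is 0.18 x 0.80 = 14.4% v 0.18 x 0.88 = 15.8%, and a finding for OPT is not false. With return reversed the figure is 0.9%.
- The doubt about wording rests on one summary phrase in II.B. Hypotheses 1 and 2, Aim 2, II.C and the schedule of events all refer to verified abstinence.

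**Conclusion.** No change to the plan is needed. It leaves a convention unstated, but its wording points one way: participants compared as randomised, 196 per arm in the power calculation, and an outcome that cannot be met without verification. An analyst following it would count all 392 as assigned, with an unverified participant not abstinent. On that reading the 90% power and the sample size stand, and no rule that the plan does state has been shown to give a wrong answer.

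What remains is a possible change between significant and not significant near p = 0.05: 0.8% of trials at equal 88% return, about 4% at a 4-point gap and 7-11% at an 8-point gap. This rests on the design rates holding among all randomised and on return rates that the documents do not give. A smaller true effect raises the figures (17-20% at a true OPT rate of 27% and an 8-point gap), but that too requires an imbalance which nothing in the plan predicts. If 18% and 32% were meant as rates among returners, which is the less natural reading, power would be 84-85% at 88% return.

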- 2) (Mediators/Moderators): Identify mediators and moderators of the relationship between treatment (OPT, UC) and verified abstinence at week 12.** Hypothesis 3. Treatment engagement (medication use, counseling attendance), experience of side effects, and change in withdrawal, craving, reinforcing effects of nicotine, positive and negative affect, and self-efficacy to refrain from smoking will mediate the relationship between treatment and abstinence. Hypothesis 4. Gender, age, socioeconomic status (SES), nicotine exposure, menthol, and nicotine dependence will moderate the relationship between treatment and abstinence.
- 3) (Process): Describe the response profile for each optimization pathway (OPT only).** There are 4 pharmacotherapy pathways that participants in OPT will potentially follow. We will describe the process of optimization including the proportion that 1) follow each OPT pathway, 2) re-initiate pharmacotherapy following changes in medication, 3) set new TQDs following changes in medication, and 4) demonstrate verified abstinence. We will also describe changes, by pathway, in responses that are predictive of treatment success/failure including withdrawal, craving, reinforcing effects of nicotine, quitting self-efficacy, positive/negative affect, and post-optimization medication use.

B. Background and Significance

African American (AA) smokers disproportionately impacted by tobacco. Tobacco remains the leading cause of preventable morbidity and mortality in the United States, accounting for more than 480,000 total deaths and more than 34% of all cancer death annually.¹ Although AA smoke fewer days per month, fewer cigarettes per day (CPD), and are less likely to be heavy smokers than Whites, they bear a disproportionate share of tobacco-attributable morbidity and mortality.² AA are at higher risk for nearly all smoking-related chronic diseases compared to Whites, have twice the rate of premature death attributable to cardiovascular disease, the highest incidence rates for all cancers combined, and higher overall cancer mortality rates compared to other racial/ethnic groups.^{3,4} With regard to smoking-attributable lung cancer, specifically, AAs have a striking 43-55% higher relative risk compared to Whites with this difference being most pronounced at lower levels of daily cigarette consumption.⁵

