
 • Non-Hispanic African American • \geq 18 years of age • Smoke 5-30 CPD • Daily cigarette smoker • Smoked at current rate for \geq 6 months • Verified smoker (CO \geq 5 ppm) • Functioning telephone • Interested in quitting smoking • Willing to take NP, VAR, and/or BUP+NP for 18 weeks and complete all study visits 	
 • Use of non-cigarette tobacco products in past 30 days • Medical contraindications to NP, BUP, or VAR: unstable cardiac condition (e.g., unstable angina or AMI) cardiac event, or stroke in the past 4 weeks; renal impairment; medications contraindicated; history of clinically significant allergic reactions; history of epilepsy, seizure, head trauma, psychosis, bipolar disorder, eating disorder; unstable panic disorder or depression; active suicidal ideation; treatment for alcohol or drug dependence in the past year • Use of pharmacotherapy in the month prior to enrollment • Pregnant, contemplating getting pregnant, or breastfeeding • Unstable housing (e.g., street, shelter) • Plans to move from KC during the treatment and follow-up phase • Another household member enrolled in the study

Inclusion criteria

Inclusion criteria are displayed in the adjoining table. Participants must smoke 5-30 CPD to be consistent with packaging guidelines for NP and minimize possible confounds in treatment response based on extreme light (1-4 CPD) or heavy (31+ CPD) smoking. The majority of AAs smoke 5-10 CPD and, combined, our CPD eligibility criteria encompasses \sim 85% of AA smokers.

Exclusion criteria

Exclusion criteria are also displayed in the adjoining table. Exclusion criteria are consistent with contra-indications for NP, BUP, and VAR.^{13,14,86-93} Non-daily smokers and those who have used non-cigarette tobacco products in the past 30 days (e.g., cigars, cigarillos) will be excluded because NP, BUP, and VAR have not been tested in these subgroups.

Withdrawal/Termination Criteria

There are no expected circumstances in which the subject's participation will be terminated by the investigator.

Clarify whether a study subject may participate in another research study while participating in this research study

Subjects are not able to participate in another smoking cessation research study while they are enrolled in the current study.

E. Specific methods and techniques used throughout the study

Laboratory tests

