Not more than 20 ml of urine will be collected four times throughout the study. At Week 0 the urine will be used for the analysis of total nicotine equivalents (TNE) and other chemicals found in cigarettes. At Wks 12, 18 and 26 the urine samples will provide biochemical verification of cessation (via urine anabasine and anatabine, with the recommended cut-off of 2 ng/ml to

[figure not shown]
differentiate smokers from non-smokers). Not more than 20ml of saliva will be collected at Week 0 for genetic analysis. The DNA analysis will be used for research to understand nicotine metabolism genotype and phenotype. Melanin will be assessed at Wk 0 using a skin reflectometer.

Study Procedures:

Intervention

All eligible participants who provide written informed consent and complete the baseline survey will be randomized in a 1:1 fashion to either OPT or UC.

Optimization Overview. The optimization flow diagram is displayed in Figure 1. Both groups will receive 18 weeks of pharmacotherapy according to standard dosing guidelines^{6,49} but the type of pharmacotherapy will vary depending on group assignment and response. **Path A** is participants randomized to enhanced UC who will receive 18 weeks of NP (Wks 0-18). **Path B1** is OPT participants who respond to NP (CO LTE 5 ppm) at each optimization time point and, therefore, remain on NP for 18 weeks (Wks 0-18). **B2** is OPT participants who respond to NP at Wk 2 but who demonstrate non-response to NP at Wk 6 (CO GT 5 ppm) and are switched to VAR. Participants in this group will receive 6 weeks of NP (Wks 0-6) and 12 weeks of VAR (Wks 6-18). **B3** is OPT participants who were switched to VAR at Wk 2 after non-response to NP and who demonstrate response to VAR at Wk 6. Participants in this group will receive 2 weeks of NP (Wks 0-2) and 16 weeks of VAR (Wks 2-18). **B4** is OPT participants who were switched to VAR at Wk 2 and BUP +NP at Wk 6. Participants in this group will receive 2 weeks of NP (Wks 0-2), 4 weeks of VAR (Wks 2-6), and 12 weeks of BUP +NP (Wks 6-18).

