Beginning March 23, 2020 and for the duration of the "COVID-19 Stay at Home Order" all face-to-face encounters will be temporarily terminated. All previous in-person assessments will be completed over the phone. Urine samples will be either mailed in or left outside for pickup by study staff as determined by location and abilities of the study participant. Medication will be dispensed similarly; either by mail or dropped at the study participant's home. Instructions and counseling sessions will be completed by phone and/or facetime. Because enrollment activities cannot be completed remotely, study enrollment will be temporarily suspended.

When the 'Stay at Home Order' is lifted or COVID-19 precautions are no longer deemed necessary, the original study protocol will go into effect.

Overview of Major Study Events and Measures

	Screen	Enroll							Primary Endpoint	EOT	Follow-Up
	-2*	0	1*	2	3*	6	7*				
	WEEKS										
Screening	X	X									
Intervention			X	X	X	X	X	X			
Counseling			X		X		X		X		
Medication Dispensing			X			X			X		
Smoking Abstinence											
CO		X		X		X					
Urine for TNE & Anabasine/Anatabine		X							X	X	X
Saliva		X									
Mediators											
Withdrawal		X	X	X	X	X	X	X	X	X	
Craving		X	X	X	X	X	X	X	X	X	
Reinf effects of nicotine		X	X	X	X	X	X	X	X	X	
Pos & Neg Affect		X	X	X	X	X	X	X	X	X	
Self-efficacy		X	X	X	X	X	X	X	X	X	
Side effects			X	X	X	X	X	X	X	X	
Medication use			X	X	X	X	X	X	X	X	
Counseling completion		X	X	X	X	X	X	X			
Moderators (all assessed at baseline)											
See measures			X								
Process Measures (OPT only)									X		
# down each OPT path										X	
# reinitiating medication						X		X			
# setting new TQD					X		X				
Verified abstinence									X	X	X
Change in withdrawal, craving, reinf effects of nicotine, affect, and self-efficacy post-optimiz.				X	X	X	X	X			
Descriptive Measures (all assessed at baseline)											
See measures			X								
Visit Length (in minutes)	30	120	45	60	45	60	45	120	45	45	

*phone visit; all other visits are in-person

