For participants who agree to future testing, samples will be stored indefinitely. New markers of nicotine and carcinogen exposure and genetic differences in nicotine metabolism are being discovered and the stored biological samples would be used for analysis of these new markers. All samples stored for future biomarker analyses will be de-identified and accessible only to members of the study team. Results from these analyses will be de-identified and shared only with members of the research team. Any resulting publications will present the data in aggregate; individual participants will not be identified.

D. Procedures to protect subject confidentiality

Confidentiality will be maintained by assigning each participant a study identification number and numerically coding all data. All biological samples and survey data will be labeled with the study identification number and never with the participant's name or other identifiable information. The association of the ID-code and the participant's name will be kept by [name] in a locked file cabinet and will only be accessible to members of the study team.

E. Quality Assurance / Monitoring

All data will be directly entered into our electronic data capture system (i.e., RedCap or CRIS) that contains edit checks to control the quality and completeness of data entry. Completeness of data entry will be automatically verified before each assessment is completed. The electronic data capture system is behind the KUMC secure firewall with role-based access that is HIPAA and human subjects compliant. There are no plans for ongoing third-party monitoring.

V. Data Analysis and Reporting

A. Statistical and Data Analysis

See II.C. above (Sample Size, Statistical Methods, and Power Calculations)

B. Outcome

See II.C. above (Sample Size, Statistical Methods, and Power Calculations)

C. Study results to participants

Study results will not be shared with participants.

D. Publication Plan

We plan to publish results in appropriate tobacco journals – e.g., JAMA, JNCI, Journal of General Internal Medicine, Addiction, Annals of Behavioral Medicine, Nicotine & Tobacco Research, Cancer Epidemiology, Biomarkers, & Prevention.

VI. Bibliography / References / Literature Cited

1. American Cancer Society. *Cancer Facts & Figures for African Americans, 2016-2018*. Atlanta, GA: American Cancer Society;2017.

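### Randomization is stratified by sex but the only efficacy test named is an unadjusted chi-square; that test is valid, and pre-specifying adjustment for sex and a few baseline variables is a cheap improvement

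*Combined protocol and SAP*

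**What the plan says.** Section II.C sets a 1:1 allocation of 392 participants and stratifies it: "Randomization will be stratified based on to ensure an equal proportion of male and female smokers in OPT and UC". The name of the factor has dropped out of the sentence, but the stated purpose identifies sex. Baseline data come before assignment: "After baseline data collection has been completed, the research assistant will select the sequential study ID number to determine the randomization assignment". The Intervention text in II.E agrees: "All eligible participants who provide written informed consent and complete the baseline survey will be randomized in a 1:1 fashion".

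The primary endpoint is verified 7-day abstinence at Week 12, with 18% expected in UC and 32% in OPT. The one efficacy test named appears in the sample-size calculation: "Using the chi-square test, along with 18% and 32% cessation rates, 196 participants in each group will give us 90% power". Section V.A, where the analysis would normally be set out, reads "See II.C. above (Sample Size, Statistical Methods, and Power Calculations".

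Baseline characteristics enter the plan only through Aim 2, Hypothesis 4: "Gender, age, socioeconomic status (SES), nicotine exposure, menthol, and nicotine dependence will moderate the relationship between treatment and abstinence". The table of study events has the row "Moderators (all assessed at baseline", so these variables are collected before treatment starts. Nowhere are they named as adjustment covariates for the primary comparison.

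**The concern.** Sex was thought important enough to stratify on, but the plan does not say whether the analysis uses it. Because V.A defers to II.C, the power sentence is the nearest thing to a primary analysis. Two things are at stake, both modest.

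- **Power.** If the chi-square is also the primary analysis, it leaves unused any predictive information in baseline data that will be collected anyway.
- **Pre-specification.** A crude chi-square, a sex-stratified test, or a logistic model with any of several covariates could each be reported as consistent with the protocol. With six candidate moderators already listed, that freedom is real. Fixing the model and covariates now removes it.

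**Working it through.** **Inputs from II.C.** UC 18%, OPT 32%, 196 per arm, type I error 5%, chi-square. Sidedness is not stated.

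**Step 1: the plan's own figure.** The mean rate is (0.18 + 0.32)/2 = 0.25.

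- Standard error under the null: sqrt(2 × 0.25 × 0.75/196) = 0.0437.
- Standard error under the alternative: sqrt((0.18 × 0.82 + 0.32 × 0.68)/196) = sqrt(0.3652/196) = 0.0432.
- Pooled power: Φ((0.14 − 1.96 × 0.0437)/0.0432) = Φ(1.257) = 89.6%.
- Unpooled power: Φ(0.14/0.0432 − 1.96) = Φ(1.283) = 90.0%.
- Unpooled sample size: (1.960 + 1.282)² × 0.3652/0.14² = 195.8, which rounds up to 196 per arm.

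The 90% reproduces two-sided. A one-sided test would give 94.3%.

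**Step 2: is the unadjusted test valid under stratification?** Trials were simulated with 98 men and 98 women per arm, no treatment effect (both arms at 18% or both at 25%), and sex-outcome odds ratios from 1 to 3. The chi-square rejected in 4.4% to 5.1% of trials and the sex-stratified Cochran-Mantel-Haenszel (CMH) test in 4.9% to 5.1%. The chi-square is at nominal level, or slightly conservative if sex is strongly prognostic.

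**Step 3: adjusting for sex alone** (assumed odds ratios; 1,000,000 simulated trials per cell at 18% vs 32%).

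| Sex odds ratio | 1 | 1.5 | 2 | 3 |
|---|---|---|---|---|
| Chi-square power, balanced within sex | 89.80% | 89.97% | 90.08% | 90.46% |
| CMH power, balanced within sex | 89.69% | 90.02% | 90.38% | 91.23% |
| Change (points) | −0.1 | +0.05 | +0.3 | +0.8 |
| Change if not blocked within sex (points) | −0.1 | +0.1 | +0.5 | +1.3 |

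**Step 4: adding baseline covariates.** The model is logistic, with arm, sex and three independent normal covariates. The marginal rates were held at 18% and 32%, and each trial was also analysed by chi-square. There were 200,000 trials at SD 0 and 30,000 in each other cell; the paired simulation error is 0.03 to 0.15 points. SD means the standard deviation of the covariates' combined contribution to the log-odds of abstinence in UC; an SD of 1.0 is an odds ratio of e¹ = 2.7 per SD. Hypothesis 4 expects moderation without giving a direction, so unequal slopes are shown too.

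| Change in power (points) | SD 0 | 0.3 | 0.5 | 0.7 | 1.0 |
|---|---|---|---|---|---|
| Equal slopes | −0.2 | +0.3 | +1.0 | +2.3 | +3.6 |
| OPT slopes halved | – | 0.0 | +0.4 | +1.2 | +2.0 |
| OPT slopes zero | – | −0.2 | +0.2 | +0.4 | +0.8 |
| OPT slopes 1.5 times UC | – | +0.5 | +1.6 | +2.8 | +5.0 |

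A separate simulation (20,000 trials) with sex and one baseline score agrees. Odds ratios of 1, 1.5, 2 and 2.5 per SD (log-odds SD 0, 0.41, 0.69 and 0.92) gave −0.1, +0.7, +2.0 and +3.5 points.

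**Step 5: participant equivalents for equal slopes, by the pooled formula of Step 1.** The n per arm that gives the same change for the chi-square is:

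- −0.2 points: about 194, so 2 × (194 − 196) = about −4 in total.
- +0.3: 198, or +4.
- +1.0: 203, or +14.
- +2.3: 213 to 214, or +34 to +36.
- +3.6: 225, or +58.

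**Step 6: does the adjusted analysis behave?** With both arms at 18% (40,000 trials per cell), the arm coefficient rejected in 4.9% to 5.1% of trials and the chi-square in 4.9% to 5.2%. The 95% interval for the standardized risk difference excluded zero in 5.2% to 5.4%. At 18% vs 32% its coverage was 94.5% to 95.0%. The p-value and the interval disagreed in 0.2% to 0.5% of trials, almost always with the interval excluding zero while p was above 0.05.

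**The case against.** The strongest reply is that nothing is broken. A chi-square on a 14-point difference is simple, valid and correctly powered, and choosing it is legitimate. One sentence naming it as the primary test would close the specification gap without any covariates. This stands, and it is why the point is an improvement only.

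It also stands that the stratifier contributes almost nothing by itself. The +0.8 points need a sex odds ratio of 3, which nothing in the documents supports. Any material gain comes from the other covariates, and their strength is assumed. At SD 0 adjustment loses slightly, and with OPT slopes at zero it is worth less than one point at every strength shown. The logistic model further separates the p-value (a conditional odds ratio) from the reported estimate (a marginal risk difference).

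What does not follow is that the change is pointless. The worst loss is about 0.2 to 0.3 points. The possible gain is several times that, needs no new data, and comes with a fixed model.

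Some stronger readings are tempting but unsupported.

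- A reader might infer that stratifying and then testing without adjustment inflates false positives or invalidates the power statement. Steps 1 and 2 show neither.
- A reader might take the eligibility limits on cigarettes per day (CPD), set to "minimize possible confounds in treatment response based on extreme light (1-4 CPD) or heavy (31+ CPD) smoking", as evidence that CPD will predict abstinence only weakly. Section II.D says the 5-30 range covers about 85% of African American smokers, and the documents give no association between CPD and abstinence. The limits do not show where in the range CPD would fall.
- A reader might treat the Hypothesis 4 variables as established predictors. They are listed as hypothesised moderators, with no strengths given.

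**Conclusion.** The point holds as a low-cost improvement. The plan stratifies by sex, names only an unadjusted chi-square, and does not state a primary model apart from the power sentence. The chi-square is valid, the 90% power is right, and 196 per arm does not change.

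The likely benefit runs from nothing to a few points of Week 12 power. It is about −0.1 to +0.8 points for sex alone with balance within sex (up to +1.3 without blocking). With three further covariates and equal slopes it is about −0.2 to +3.6 points. It falls to about −0.2 to +0.8 if those covariates do not predict outcome in OPT. These figures rest on the planned 18% and 32% and on assumed prognostic strength, so the range should be read as a whole. No gain is claimed for Weeks 18 and 26, for which the documents give no rates. The firmer benefit is that the model and covariates are settled before outcomes are seen.

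**What to change.** Add to II.C, in the sponsor's own words, that:

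- the primary Week 12 analysis is a logistic regression of verified abstinence on arm, sex (the stratifier) and a short list of already-collected baseline variables, fixed before any outcome data are examined (for example nicotine dependence, CPD and age);
- the arm effect is tested two-sided at 5%;
- the effect is reported as a standardized risk difference with its 95% confidence interval, with a note that the p-value comes from the arm coefficient and may occasionally disagree with the interval;
- a sex-stratified CMH test replaces the model if it does not converge;
- the unadjusted chi-square is kept as a sensitivity analysis.

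The cost is a few sentences and slightly more analysis work, with no new data, visits or participants. About 0.2 to 0.3 points of power are lost if the covariates turn out not to predict abstinence. In about 0.2% to 0.5% of trials the p-value and the interval would point different ways.
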